#### 9.2 **SECONDARY OBJECTIVES**

- Influence of patient characteristics on diagnostic accuracy of Thermalytix™.
  Patient characteristics will include:
  - Age
  - Lesion type
  - Pathologic diagnosis
  - Menopausal and hormonal status
  - Breast density
  - Family history
- 2. Recommend how Thermalytix™ can be used to complement standard breast cancer screening procedure.

16 Sep 2020 Confidential Page 20 of 53

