## iii. Secondary Effectiveness Analyses

Influence of patient characteristics such as age group, menopause status and breast density on diagnostic accuracy (sensitivity, specificity, PPV and NPV) of Thermalytix™ as compared to that of standard modalities were reported along with 95% confidence interval.

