# 10.7.2 Determination of Sample Size

The sample size was calculated with two-sided 95% confidence interval (CI) for a sample sensitivity and target width of 0.5 using Clopper-Pearson Interval (Exact) Method. The prevalence of breast cancer and other breast abnormalities in Indian women during their lifetime was assumed to be 4% (1 in 25 were expected to have a breast abnormality in their lifetime in India). A sample size of 300 screening patients allows estimating the true prevalence by means of an exact 95% confidence interval with width of 0.487 percent points when the sample sensitivity was assumed to be 80%. Considering exclusions from data analysis due to multiple visits needed, over 600 women were recruited. Eventually, data of 459 women could be used for statistical analysis as they satisfied inclusion criteria and adhered to the study protocol.

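### The objective on influence of patient characteristics has no between-level contrast for Thermalytix accuracy and nothing that separates age, menopause and breast density

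*Combined protocol and SAP*

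**What the plan says.** The first secondary objective in section 9.2 is "Influence of patient characteristics on diagnostic accuracy of Thermalytix™". Six characteristics are listed there: age, lesion type, pathologic diagnosis, menopausal and hormonal status, breast density and family history.

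Section 10.7.1 iii turns this into an analysis. It names age group, menopause status and breast density as examples, and says that sensitivity, specificity, PPV and NPV of Thermalytix "as compared to that of standard modalities were reported along with 95% confidence interval". The general text of section 10.7.1 attaches a 95% interval to each accuracy measure.

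No section specifies a difference between levels of a characteristic, an interaction, a regression model, an adjustment of one characteristic for another, or a rule for concluding that a characteristic matters. That the intervals are one per subgroup is an inference from section 10.7.1; it is not written. On numbers, section 10.7.2 states: "Eventually, data of 459 women could be used for statistical analysis".

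**The concern.** Influence means that accuracy differs between levels of a characteristic. The comparison that section 10.7.1 iii does name is between tests, Thermalytix against standard modalities. Even if it is made within each subgroup, it does not estimate how far Thermalytix itself changes from one level to another.

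Two consequences follow. First, a reader left with one interval per subgroup may decide by whether the intervals overlap, which is a much stricter criterion than a 5% comparison. Real differences in the false-positive rate could then be passed over. Second, the Introduction explains the lower sensitivity of mammography in younger women by their denser tissue, so age and density are expected to travel together. Looked at one at a time, an apparent age effect may be a density effect. Both matter for the other secondary objective, a recommendation on how Thermalytix can complement standard screening, because that depends on knowing in which women it performs differently.

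**Working it through.** **Inputs from the documents (section 10.7.2).** Two-sided 95% level; assumed sensitivity 80%; assumed prevalence 4%; 300 women planned, 459 analysed.

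**The plan's own figure.** Cases = 300 × 0.04 = 12; detected = 0.80 × 12 = 9.6. The Clopper-Pearson limits from beta quantiles are 0.480 and 0.967, a width of 0.4874. This reproduces the stated 0.487. It is the only precision figure given, and it concerns overall sensitivity, not subgroups.

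**Non-malignant women.** 459 × 0.04 = 18.36, about 18 cases, leaving 459 − 18 = 441.

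**Assumptions not in the documents.** The specificity values, the subgroup shares and the link between age and density. The 4% is also used here as the prevalence of malignancy, whereas the document gives it as a lifetime figure that includes other breast abnormalities.

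**Step 1: normal approximation, two strata of 220, specificity 90% v 80%.**
- SE of the difference = √(0.9×0.1/220 + 0.8×0.2/220) = 0.0337, so the 95% half-width is 1.96 × 0.0337 = 0.066.
- Power with an interval for the difference = Φ(0.10/0.0337 − 1.96) = Φ(1.01) = 84%.
- Non-overlap needs the gap to exceed 1.96 × (0.0202 + 0.0270) = 0.0925. Power = Φ((0.10 − 0.0925)/0.0337) = Φ(0.22) = 59%.
- Type I error of non-overlap with equal standard errors = 2 × [1 − Φ(1.96 × √2)] = 0.56%.

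**Step 2: exact check.** Power is the sum of Bin(x₁; n₁, p₁) × Bin(x₂; n₂, p₂) over all outcomes where the criterion is met. The criteria are a Newcombe interval for the difference that excludes 0, and separate Clopper-Pearson intervals that do not overlap.

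| Strata | Specificity | Difference interval | Non-overlap |
|---|---|---|---|
| 220/221 | 90% v 80% | 84% | 52% |
| 132/309 (30:70) | 90% v 80% | 76% | 43% |
| 88/353 (20:80) | 90% v 80% | 61% | 31% |
| 220/221 | 95% v 90% | 50% | 18% |
| 220/221 | 80% v 70% | 68% | 33% |
| 220/221 | 90% v 90% (type I error) | 4.8% | 0.35% |

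With Wilson intervals, the 52% in the first row becomes 57%. Together with step 1, the range for non-overlap there is 52% to 59%.

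**Step 3: sensitivity.** With about 18 cases split 9/9, power for 90% v 60% is 31% with a difference interval and 1% by non-overlap. For 90% v 70% it is 14% and 0.2%. A formal contrast gains little of use here.

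**Step 4: age and density.** Suppose density alone drives specificity (80% dense, 90% non-dense), and 70% of younger and 30% of older women are dense.
- Younger: 0.70 × 80 + 0.30 × 90 = 83%.
- Older: 0.30 × 80 + 0.70 × 90 = 87%.
- Age shows a 4-point gap although it has no effect. With shares of 80% and 20% the values are 82% and 88%, a 6-point gap.

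**Step 5: what a joint model could carry.** Expected false positives among 441 women are 441 × 0.05 = 22 at 95% specificity, 441 × 0.10 = 44 at 90%, and 441 × 0.20 = 88 at 80%.

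**The case against.** The strongest reply is that the plan proposes no decision rule at all. Section 10.7.1 is about estimation: it names no test, no alpha for subgroups and no overlap criterion. Separate subgroup estimates lose no information, and anyone with the counts can compute the difference. This stands. A reader might infer from section 10.7.1 iii that influence is judged from separate subgroup intervals, and so that the plan itself wastes power. The text does not say that. Its wording is loose enough to cover several analyses, and the loss arises only if readers decide by overlap.

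A reader might also infer that an interval for the between-level difference would untangle age from density. It would not: the 4-point gap in step 4 appears in an unadjusted difference as well. Only a joint analysis addresses it, and if age and menopause are very closely related, even that may separate them poorly.

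It is also fair to say that the power figures depend on assumed specificities and splits, that the gain is modest in some of them, and that several contrasts at 5% each do not amount to an overall 5% assessment. What remains is that the plan states an objective about influence and specifies no estimate of it.

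**Conclusion.** The point holds as a gap between objective and analysis: no between-level contrast and no joint model is specified. It is worth correcting, but it is not a flaw in the primary analysis.

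The size is conditional. If influence is read from interval overlap, specificity contrasts that would have 50% to 84% power in the scenarios tabulated have 18% to 52% by exact Clopper-Pearson non-overlap. These figures rest on about 441 non-malignant women and the assumed specificities and splits. A somewhat different case count would still leave several hundred non-malignant women, so the ordering would not change. The confounding example is illustrative. The documents support the direction of the link between age and density but give no strength for it. For sensitivity, the number of expected cancers is too small for any contrast to be more than descriptive.

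**What to change.** In section 10.7.1 iii:

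- For each characteristic, report the between-level difference in Thermalytix specificity with a 95% interval (Newcombe or Miettinen-Nurminen).
- Add one logistic model for a false-positive Thermalytix call among non-malignant women, with age, menopause and breast density together. Limit the number of terms to what the observed false positives support, and state that age and menopause may separate poorly.
- Report between-level differences in sensitivity with exact intervals, labelled descriptive, and fit no interaction model on the cancers.
- Label all of this supplementary and without multiplicity control. The document is written after the event, and section 10.8.2 records no changes to the analyses, so the additions are post hoc and should be described as such.

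The cost is a little programming and wording on data already collected. The downside is that the wide intervals, above all for sensitivity, become explicit.

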### iv. Safety Analysis

Thermography measures the skin temperature remotely and hence is virtually free of any adverse side effects. Thermography is a pain-free, non-invasive examination. Thermography does not require the use of sedatives, anesthesia, or any other medications. It is passive and measures the temperature on the skin, similar to a thermometer. However, in case of any adverse events (AEs), the AEs reporting followed regulations related to spontaneous Individual Case Safety Reports management, i.e., Investigators were asked to report only related AEs (non-serious and serious) to the sponsor.

16 Sep 2020 Confidential Page 30 of 53

# 10.7.2 Determination of Sample Size

The sample size was calculated with two-sided 95% confidence interval (CI) for a sample sensitivity and target width of 0.5 using Clopper-Pearson Interval (Exact) Method. The prevalence of breast cancer and other breast abnormalities in Indian women during their lifetime was assumed to be 4% (1 in 25 were expected to have a breast abnormality in their lifetime in India). A sample size of 300 screening patients allows estimating the true prevalence by means of an exact 95% confidence interval with width of 0.487 percent points when the sample sensitivity was assumed to be 80%. Considering exclusions from data analysis due to multiple visits needed, over 600 women were recruited. Eventually, data of 459 women could be used for statistical analysis as they satisfied inclusion criteria and adhered to the study protocol.

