# 10.7 STATISTICAL METHODS PLANNED IN THE PROTOCOL AND DETERMINATION OF THE SAMPLE SIZE

#### 10.7.1 Statistical and Analytical Plans

Analysis of the data was performed by the Biostatistics and Statistical Programming team of Statiza Statistical Services. All statistical analyses were performed using R Software version 3.5.0 and SAS® Version 9.4 or higher [SAS Institute Inc., USA].

The following standard descriptive summaries were presented:

The continuous data was summarized using the number of observations (n), arithmetic mean (mean), standard deviation (SD), median, minimum value (min), and maximum value (max). The categorical variables were summarized using the frequency count (n) and percentage (%) for each possible value. The frequencies were presented up to 0 decimal places and percentage up to 2 decimal places.

Thermalytix™ and standard modalities were evaluated using following measures of validity:

- Sensitivity The probability of correctly identifying a true case of malignancy
- Specificity The probability of correctly identifying a true case of non-malignancy (normal or benign)
- Positive Predictive Value (PPV) The probability that a labelled positive was a true case of malignancy
- Negative Predictive Value (NPV) The probability that a labelled negative was a true case of non-malignancy

All the methods of validity were computed for Thermalytix™ along with their 95% CI.

16 Sep 2020 Confidential Page 29 of 53

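### Section 10.7.2 reports its precision for sensitivity (CI width 0.487) as a prevalence width in percentage points, and its case count rests on a lifetime any-abnormality rate, not on malignancy

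*Combined protocol and SAP*

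**What the plan says.** Section 10.7.2 opens by sizing the study on a Clopper-Pearson "two-sided 95% confidence interval (CI) for a sample sensitivity and target width of 0.5". It then gives the input for the number of cases: "The prevalence of breast cancer and other breast abnormalities in Indian women during their lifetime was assumed to be 4" per cent, restated as 1 woman in 25 with a breast abnormality over her lifetime. The result sentence takes 80% as the sensitivity and says that 300 screening patients suffice, because this number "allows estimating the true prevalence by means of an exact 95% confidence interval with width of 0.487 percent points". The paragraph ends with recruitment of over 600 women and the number analysed: "Eventually, data of 459 women could be used for statistical analysis as they satisfied inclusion criteria and adhered to the study protocol".

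Section 10.7.1 defines the two measures that fix who is a case: "Sensitivity The probability of correctly identifying a true case of malignancy", and "Specificity The probability of correctly identifying a true case of non-malignancy (normal or benign"). A woman with a benign abnormality therefore belongs to the specificity denominator, not the sensitivity denominator.

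**The concern.** Two things in section 10.7.2 do not fit together.

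- **Parameter and unit.** The paragraph starts with an interval for sensitivity and a target width of 0.5, then reports the result as an interval for prevalence in percentage points. Taken literally, 0.487 percentage points is 0.00487 on the 0-1 scale. That is one hundredth of the target the figure is meant to meet, and it describes a quantity the study was not sized for.
- **Case definition.** The number of cases comes from a lifetime rate of any breast abnormality. The analysis counts only malignancies as cases, found in a work-up that section 10.1 limits to two weeks. The paragraph does not mention the difference.

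Sensitivity is a primary measure (sections 9.1 and 10.7.1), and this is the only precision rationale given for the sample size. A reader who takes the sentence as written cannot tell that the design anticipated an interval for sensitivity of roughly 48% to 97%, or that this width was never derived for malignancy.

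**Working it through.** **Inputs from section 10.7.2:** N = 300, prevalence 4%, sensitivity 80%, two-sided 95%, Clopper-Pearson, target width 0.5, 459 women analysed.

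**Step 1: reproduce the plan's figure.**

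Expected cases: n = 300 × 0.04 = 12. Expected detections: x = 0.80 × 12 = 9.6. This is not a whole number, but the formula accepts it.

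- Lower limit = 2.5% quantile of Beta(x, n − x + 1) = Beta(9.6, 3.4): 0.4796
- Upper limit = 97.5% quantile of Beta(x + 1, n − x) = Beta(10.6, 2.4): 0.9670
- Width = 0.9670 − 0.4796 = 0.4874

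This matches 0.487. Twelve is also the smallest whole number of cases that meets the 0.5 target at 80% sensitivity (11 cases give 0.508), and 12 / 0.04 = 300. Both the width and N reproduce.

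**Step 2: try the other readings.**

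| Reading | Width |
|---|---|
| Prevalence, 12/300 (0.0208 to 0.0688) | 0.048 |
| Sensitivity taken over all 300 women, 240/300 | 0.094 |
| Sensitivity, 12 cases, 90% two-sided interval | 0.429 |
| Sensitivity, whole count 9/12 | 0.517 |
| Sensitivity, whole count 10/12 | 0.463 |

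None of these gives 0.487. The figure is the 0-1 scale width for sensitivity at the expected count, that is 0.487 × 100 = 48.7 percentage points.

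**Step 3: what the 4% must mean for the width to apply to malignancy.**

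The documents give no malignancy prevalence for the women screened. The Introduction gives Indian case counts (162 thousand incident, 405 thousand over five years) without a population denominator. The prevalences below are therefore assumptions, and each width is taken at the expected case count with 80% sensitivity.

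| Assumed malignancy prevalence | Width, N = 300 | Width, N = 459 |
|---|---|---|
| 1% | 0.842 | 0.734 |
| 2% | 0.663 | 0.552 |
| 3% | 0.557 | 0.456 |
| 4% | 0.487 | 0.396 |
| 5% | 0.438 | 0.354 |
| 6% | 0.400 | 0.322 |

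**Step 4: thresholds.**

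- Width 0.487 needs 12 expected cases: 12/300 = 4.0%; 12/459 = 2.6%.
- Width 0.5 needs 11.37 expected cases: 11.37/300 = 3.8%; 11.37/459 = 2.5%.

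**The case against.** The best defence is that the paragraph corrects itself. It opens with sensitivity, the exact method and a target of 0.5, and the result sentence closes with the assumed sensitivity. Beside a target of 0.5, a value of 0.487 makes sense only on the same scale. Recruitment is also complete, and section 10.7.1 requires 95% intervals that depend on the cases observed, not on this sentence. More women were analysed (459) than the 300 planned, which offsets some of any shortfall in cases.

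Most of this stands, and it keeps the point minor. It does not remove it. To be sure which quantity 0.487 describes, a reader has to recompute the interval, and rewording the result sentence would not repair the mismatch in case definition.

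Two stronger readings are tempting, and the documents support neither:

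- **That the sample size was miscalculated.** It was not: N = 300 and 0.487 both follow exactly from the stated inputs.
- **That the study was too small to estimate sensitivity for malignancy.** A lifetime any-abnormality rate might seem bound to overstate the malignancies found at screening. But section 10.3 admits any woman aged 18 or over and does not exclude current symptoms, and section 10.1 records current complaints. The proportion with malignancy among those enrolled could be below or above 4%. A loss of precision is possible but not shown.

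**Conclusion.** The point holds as a misstated parameter, unit and input assumption, not as a miscalculation. The 0.487 is the exact 95% interval width for sensitivity on the 0-1 scale: 48.7 percentage points at 12 expected cases and 80% sensitivity. Those 12 cases come from a broader, lifetime condition than the malignancy on which section 10.7.1 defines sensitivity, so the documents do not support the stated precision for malignancy. The direction and size of the effect are unknown. The thresholds of about 4% (300 women) and 2.6% (459 women) assume 80% sensitivity and the expected case count. Severity is minor.

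**What to change.** In section 10.7.2:

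(a) Replace the result sentence with:

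> Assuming that 4% of 300 women (12) are cases and that sensitivity is 80%, the exact 95% CI for sensitivity has a width of about 0.487 (48.7 percentage points; approximately 48% to 97%).

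(b) Add after it:

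> The 4% is a lifetime figure for any breast abnormality and differs from the malignancy definition in 10.7.1. At the expected case count and 80% sensitivity, the 0.487 width is reached with 300 women only if malignancy prevalence is about 4% or higher (0.5 target: about 3.8%), and with the 459 women analysed only if it is about 2.6% or higher (0.5 target: about 2.5%); it is wider if prevalence is lower.

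The sample size needs to be named in (b), because the threshold for 300 women would be wrong for the 459 analysed.

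The cost is one restated and one added sentence. Enrolment and analyses are unchanged; the only downside is that the stated precision reads less favourably.

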#### 10.8 CHANGES IN THE CONDUCT OF THE STUDY OR PLANNED ANALYSES

# 10.8.1 Changes in the Conduct of the Study

There were no changes in the planned study conduct.

## 10.8.2 Changes to the Analyses

There were no changes in the analyses before and after database lock.

16 Sep 2020 Confidential Page 31 of 53
